Title	External laboratory bio-equivalency study of the Omni and GeneXpert platforms for TB and RIF resistance detection by Xpert Ultra		
Short title	Omni Bio-equivalency Study		
Protocol version and date	V1.0		
Background and rationale	The placement of GeneXpert in peripheral settings is limited by the lack of sufficient infrastructure (i.e. stable power supply) and by variable environmental conditions (i.e. temperature and humidity fluctuations). GeneXpert Omni is a new robust platform for Xpert cartridge testing at primary healthcare facilities. The Omni device is a single module, battery-powered, point-of-care device with cloud-based connectivity for data transfer and increased stability to dust and high temperatures. Evaluation of the Omni device against the well-characterized GeneXpert platform is needed to determine the equivalency of Omni for the detection of M. tuberculosis (MTB) and resistance to rifampicin (RIF). In particular, evaluation of the Omni device under environmental stressors (i.e. high temperature and humidity) is needed to demonstrate whether the device can be used at point-of-care with equivalent performance to GeneXpert.		
Primary objective(s)	 1.1 Compare the performance of the Xpert MTB/RIF Ultra assay between the GeneXpert and Omni systems with testing of clinical specimens 1.2 Compare the performance of the Xpert MTB/RIF Ultra assay between the GeneXpert and Omni systems with testing of MMQCI controls at high temperature and humidity conditions 		
Primary endpoints (outcomes)	 Positive and negative concordance of Xpert MTB/RIF Ultra testing on Omni compared to GeneXpert for clinical specimens Positive and negative concordance of Xpert MTB/RIF Ultra testing on Omni compared to GeneXpert for MMQCI controls at different temperature and humidity conditions Average difference in Ct-values for each Xpert MTB/RIF Ultra MTBC probe when testing on Omni compared to GeneXpert for MMQCI controls at different temperature and humidity conditions Average difference in Tm values for each Xpert MTB/RIF Ultra rpoB probe when testing on Omni compared to GeneXpert for MMQCI controls at difference in Tm values for each Xpert MTB/RIF Ultra rpoB probe when testing on Omni compared to GeneXpert for MMQCI controls at different temperature and humidity conditions 		
Study design	This is an external laboratory equivalency study to evaluate the performance Xpert MTB/RIF Ultra testing on Omni compared to GeneXpert. This study will use well-characterized clinical specimens from existing sample banks to assess the positive and negative concordance between the two devices at normal environmental conditions. The study will also evaluate the positive and negative concordance between the two devices at high heat and humidity using Cepheid controls, and look at differences in Tm and Ct values between platforms for Ultra testing of the same controls at 3x Ultra LoD.		

Omni Bio-equivalency study Protocol #

Study sites/setting	San Raffaele Scientific Institute, Milan, Italy	
Study population Clinical specimens selected from the FIND specimen bank and pro MMQCI controls		rovided
Sample Size	Sample SizeObjective 1.1: Xpert MTB/RIF Ultra testing of a total of 160 MTB positi and 40 MTB negative specimens on both Omni and GeneXpert	
	Objective 1.2: Xpert MTB/RIF Ultra testing of a total of 30 replicates of the MTB WT control and 30 replicates of the MTB MDR control at 3x the Ultra LoD per each environmental condition on Omni and at baseline conditions on GeneXpert	
	One negative control will also be tested per day per Omni/Gene Xpert device.	
Study duration5 months from conception to completion, 30 days of testing.		
Time schedule Study set up (IRB approval, study agreements) Shipment of devices, samples, Cepheid controls and cartridges Testing and data reporting Start Q2 2020		8 weeks 3 weeks 6 weeks

Schedule of Activities

Procedure	Timeline	Notes
Study set up (IRB approval, study agreements)	1 December – 15 July 2020	*Cepheid Omni delay has impacted timelines. No instruments available before July
Shipment of devices, samples, Cepheid controls and cartridges	16 July – 6 August 2020	*Additional time allocated for shipments given COVID-related delays
Testing and data reporting	7 August – 18 Sept 2020	

1 Introduction

The GeneXpert Omni system ('Omni') is a single-cartridge, battery-powered, point-of-care platform for rapid, onsite molecular tuberculosis testing at primary care clinics in high burden countries.

The study described herein is an external, laboratory study to investigate the equivalency of Xpert MTB/RIF Ultra testing on the Omni platform compared to the GeneXpert platform.

1.1 Trial Rationale

A well-controlled laboratory evaluation study is needed to evaluate the performance of Xpert MTB/RIF Ultra testing on the Omni system compared to the GeneXpert platform to ultimately determine platform concordance for the detection of *M. tuberculosis* (MTB) and resistance to rifampicin (RIF). An evaluation of Xpert MTB/RIF Ultra testing on the Omni device under high temperature and humidity conditions is also needed to support the use of the platform at the point-of-care in settings of intended use.

1.2 Background

There are 10 million incident cases of tuberculosis (TB) annually, though it is estimated that 3 million of these cases go undiagnosed each year¹. Additionally, the emergence of multi- and extensively drug-resistant TB (M/XDR-TB) is a major threat to global TB control. Standard phenotypic methods for TB diagnosis are inadequate, as culture and conventional drug susceptibility testing (DST) using media such as Lowenstein–Jensen and Middlebrook 7H10/11 can take up to 8-12 weeks to return results², and even liquid-based culture techniques such as MGIT® (BD Diagnostics) still take several weeks³. The delays associated with culture-based DST lead to prolonged periods of ineffective TB therapy and ongoing transmission. In view of the inadequate diagnosis and increasing incidence of M/XDR-TB, the development of rapid molecular diagnostic tests for the identification of MTB and the detection of drug resistance has become a research and implementation priority.

The Xpert® MTB/RIF Assay ('Xpert') provides a result for TB and RIF resistance detection in a sputum sample within 2 hours with minimal hands-on time^{4,5}. Xpert sensitivity for TB detection is 98% for smear-positive and 67% for smear-negative TB, with a specificity of 99% based upon 27 studies with close to 10,000 participants. The assay detects RIF resistance with 95% sensitivity and 98% specificity⁶. In 2010, WHO endorsed Xpert for use as the initial diagnostic test in individuals suspected of MDR or HIV-associated TB, and in 2014 expanded this recommendation for use in all patients, given adequate resources⁷. The Xpert MTB/RIF Ultra assay, incorporating two different multicopy amplification targets (IS6110 and IS1081) and using a renewed assay chemistry coupled with a larger DNA reaction tube, has improved upon the Xpert MTB/RIF assay, demonstrating enhanced accuracy for RIF resistance detection and greatly improved sensitivity compared with that of Xpert in smear-negative, culture-positive TB and HIV-associated TB

Omni Bio-equivalency study Protocol # TB046-bioequiv1.0 meningitis^{8,9}. These assays have since been widely used in TB programmes, but diagnostic gaps remain, especially at lower-level healthcare facilities.

The placement of GeneXpert in peripheral settings is limited by a lack of sufficient infrastructure (i.e. stable power supply) and by extreme environmental conditions¹⁰. The GeneXpert Omni is a new, robust platform to allow Xpert MTB/RIF or Ultra testing at primary healthcare facilities. The Omni device is a single-module, battery powered, point-of-care device with cloud-based connectivity for data transfer. The device has increased stability to dust and high temperatures. To date, alpha prototype units of the Omni system have undergone preliminary assessments of the user interface and connectivity features in Malawi and South Africa, and verification and validation of the Omni instrument and its associated software (including its performance against GeneXpert) will be performed by the manufacturer. An external, laboratory study conducted independently of the manufacturer is also needed to assess the equivalency of the Omni platform compared to GeneXpert.

1.3 Benefit/Risk Assessment

No participants will be recruited during this study and so no risks are expected. In contrast, the knowledge gained from this study will potentially benefit society by improving TB and drug resistance detection.

2 Study Objectives and Endpoints

The aim of the study is to assess whether Xpert MTB/RIF Ultra testing on the Omni platform is equivalent to Xpert MTB/RIF Ultra testing on the GeneXpert platform.

Objectives	Outcomes
Primary	
1.1 Compare the performance of the Xpert MTB/RIF Ultra assay between the GeneXpert and Omni systems with testing of clinical specimens	1.1 Positive and negative concordance of Xpert MTB/RIF Ultra testing on Omni compared to GeneXpert for clinical specimens
1.2 Compare the performance of the Xpert MTB/RIF Ultra assay between the GeneXpert and Omni systems with testing of MMQCI controls at high temperature and humidity conditions	1.2 Positive and negative concordance of Xpert MTB/RIF Ultra testing on Omni compared to GeneXpert for MMQCI controls at different temperature and humidity conditions
	1.3 Average difference in Ct-values for each Xpert MTB/RIF Ultra MTBC probe when testing on Omni compared to GeneXpert for MMQCI controls at different temperature and humidity conditions
	1.4 Average difference in Tm values for each Xpert MTB/RIF Ultra rpoB probe when testing on Omni compared to GeneXpert for MMQCI controls at different temperature and humidity conditions

3 Study Design

3.1 General Design

This is an external, laboratory-based equivalency study of the Cepheid GeneXpert and Omni platforms. This study will use banked clinical specimens to assess the positive and negative concordance between the two devices. The study will also evaluate the Omni device performance upon testing of Xpert MTB/RIF Ultra cartridges in comparison to GeneXpert for high temperature and humidity conditions using MMQCI controls, assessing the positive and negative concordance between the two devices at 3x the Ultra LoD given different environmental and determining the average difference in Ct-values or Tm values for each Xpert MTB/RIF Ultra probe, as appropriate.

3.2 Scientific Rationale for Trial Design

This external, well-controlled laboratory assessment study will provide equivalency data for testing of Xpert MTB/RIF Ultra on the Omni platform compared to GeneXpert under controlled environmental conditions as well as high temperature and humidity conditions. The evaluation will be carried out independently of the manufacturer at San Raffaele Scientific Institute, Milan, Italy.

4 Strain selection and Eligibility

For the equivalency assessment that is carried out at controlled environmental conditions, FIND will provide the site with a set of clinical specimens from the FIND specimen bank. The selection will include 160 MTB culture-positive raw sputum specimens. Forty MTB culture-negative sputum specimens will also be provided by San Raffaele for this assessment. The rationale for using raw clinical specimens is that (a) the specimens are well characterized and (b) it allows for end-use testing of the platforms (i.e. testing of clinical sputum samples).

For the equivalency assessment that is carried out at high environmental conditions, Cepheid will provide the site with aliquots of controls (Appendix 2: MTBC-positive wildtype, MTBC-positive MDR and MTBC-negative). Each environmental condition will be tested by 30 replicates of the wildtype control and 30 replicates of the MDR control at the Ultra LoD. Daily negative control testing will be performed per GeneXpert and Omni device. The rationale for using Cepheid controls instead of clinical specimens for this assessment is that (a) high environmental (i.e. temperature and humidity) conditions, rather than the DNA extraction process itself, are a challenge for the assay and (b) controls will introduce less variability as the bacillary load can be controlled.

5 Investigational products

5.1 Investigational Product

The investigational product used in this study is the GeneXpert Omni platform. The Xpert MTB/RIF Ultra assay will be tested on this platform for the detection of *M. tuberculosis* and resistance to RIF. The comparator product used in this study is the GeneXpert platform.

Instructions for use of the investigational product(s) are provided by the manufacturer.

Medical device incidents, including those resulting from malfunctions of the device or IVD assay must be detected, documented and reported by the investigator at each site throughout the trial (see Study Manual).

5.2 Preparation/Handling/Storage/Accountability

The investigational products will be strictly accounted for, including receipt and inventory, storage, use during the trial, and return or disposal, as detailed in the Manual of Procedures.

Acquisition

Procurement of the investigational products will be done through FIND, who will coordinate shipments from the manufacturer. It is the responsibility of the study site to maintain an updated inventory of the study materials and to inform FIND immediately if additional materials are required.

The investigator or designee must confirm appropriate temperature conditions have been maintained during transit for the investigational product received and any discrepancies are reported and resolved before its use.

Storage

Procedures for product storage and disposal will be described in the Study Manual.

The investigational product must be stored in a secure, environmentally controlled, and monitored (manual or automated) area in accordance with the labelled storage conditions with access limited to the investigator and authorized site staff. Expired or unused investigational materials will either be discarded or returned to the manufacturer, per manufacturer instructions.

Test Handling and Performance

Testing using the investigational products will be performed according to the manufacturer's instructions and as further outlined within the Study Manual.

Accountability

The investigator is responsible for trial intervention accountability, reconciliation, and record maintenance (i.e., receipt, reconciliation, and final disposition records). Investigational Product Accountability logs filled at each site will ensure the proper follow-up of the used, failed and remaining investigational products

Omni Bio-equivalency study Protocol # TB046-bioequiv1.0 Further guidance and information for the final disposition of unused investigational product are provided in the Study Manual.

Export and Import Permits

It is expected that most countries will require import permits for receiving the investigational materials. Local sites are responsible for making import permit applications in a timely manner.

Quality Control Check for Incoming Shipments

Upon arrival of each new shipment of assays, the sites will conduct and document an incoming quality check following the Study Manual. New lots may only be used after this quality check is successfully passed.

Local procurement

The investigational site is responsible for assessing its needs and procuring any supplies, reagents and kits needed for the study that are locally available in order to include these costs in the study budget, other than the supplies of the assays under investigation, which will be supplied free of charge by the manufacturer.

It is expected that the investigational site will require import permits for receiving the investigational products. The site is responsible for making import permit applications in a timely manner.

It is the responsibility of sites to conduct and document incoming quality check for each new shipment upon arrival and following the study manual. Incoming quality check includes visual inspection of the materials and a check that materials were received at conditions specified by the manufacturer as well as successful testing of external controls. New lots and new shipments may only be used after this quality check is successfully passed.

5.3 Minimisation of Error and Bias

For the equivalency assessment of Omni against GeneXpert at controlled environmental conditions, each sputum specimen will be prepared and split into two aliquots, then randomized (see section 6: Study procedures) and loaded into two Xpert MTB/RIF Ultra cartridges. One cartridge will be tested using GeneXpert and one using Omni. In this way, both devices will be tested with the same sample and there is no risk that any of the two devices will be tested on a higher-quality or more concentrated sample.

Cepheid controls will be used for the equivalency assessment of the Omni at high environmental conditions (i.e. high temperature and humidity). There is therefore minimal risk that any of the two devices will be tested on a higher-quality or more concentrated sample.

Compiling molecular test results harbours little risk of review bias, as results output from Xpert MTB/RIF Ultra testing is automatic, not requiring manual reading or user interpretation.

6 Study Procedures

Trial procedures and their timing are summarized in the Schedule of Assessments. Protocol waivers or exemptions are not allowed.

Adherence to the trial design requirements, including those specified in the Schedule of Assessments, is essential and required for study conduct.

6.1 Study workflow

[figure not shown]
The study flow is shown in Figure 1.

FIND will ship the required clinical specimens selected for this study to the investigational site. Cepheid will ship the platforms, cartridges, and MMQCI controls required for this study to the site.

For the equivalency assessment of Omni against GeneXpert at controlled environmental conditions, each clinical specimen will be prepared, homogenized and split into two equal aliquots for Xpert MTB/RIF Ultra testing. The two Xpert MTB/RIF Ultra cartridges will be randomized for testing, with one cartridge tested using the Omni platform and one cartridge tested using the GeneXpert platform at room temperature conditions.

For the equivalency assessment that is carried out at high environmental conditions, Xpert MTB/RIF Ultra cartridges will be stored at the respective temperature and humidity conditions for 72 hours prior to testing. Each environmental condition will be tested by Omni using 30 replicates of the wild type control and 30 replicates of the MDR control at 3x the Ultra LoD. GeneXpert testing using Xpert MTB/RIF Ultra will also be performed using 30 replicates of the wild type control and 30 replicates of the Ultra LoD. Four Omni systems will be used for testing at each environmental condition. Daily negative control testing will also be performed for each device.

Figure 1: Sample workflow

*30 replicates of each control will be tested by each platform at the listed conditions (i.e. 30 replicates per condition) at 3x LoD. Replicate testing will be divided between 4 Omni instruments. Daily negative control testing will also be performed for Omni and GeneXpert. **Ultra cartridges to be stored at respective condition (20-25C, 50% RH or 35C, 90% RH) for 72hr prior to testing

6.2 Panel and strain, Handling, Transport and Storage

The raw clinical specimens contain live and pathogenic *M. tuberculosis* strains that were collected from tuberculosis patients. Processing of the clinical specimens requires BSL-3 facility. Frozen aliquots of clinical specimens must be stored at -80°C.

Cepheid-provided MMQCI controls (Appendix 2) should be stored at 2-8°C upon receipt and after opening. These controls should not be frozen. Unopened controls are stable through the expiration date printed on each bottle when stored at $2^{\circ} - 8^{\circ}$ C. Opened material tightly capped and returned to the refrigerator ($2^{\circ} - 8^{\circ}$ C) shortly after use is stable for thirty (30) days from the date of opening.

6.3 Comparator Test and Index Test Procedures

Xpert MTB/RIF Ultra testing on the GeneXpert and Omni platforms will be performed based on the instructions provided by the manufacturers. Additional work instructions will be prepared by FIND to standardise any areas open to interpretation or variability including sample handling and labelling, sample randomization, quality assurance, training, recording and reporting, and instrument verification.

6.4 Safety Assessments

No safety assessment will be done since no incidents are expected upon use of the different assays (see section 7).

7 Safety and Incident Reporting

Safety and/or incident reporting is not applicable for this study. No participants will be enrolled during this study and the investigational products are non-invasive molecular assays. Therefore, no safety and/or incident reporting is expected during this study.

8 Statistical Considerations

8.1 Statistical Analysis Plan

Given the study design, no detailed statistical analysis plan (SAP) will be prepared for this work. Rather, dummy tables for results reporting will be provided and only some key elements are presented here. This section is a summary of the planned statistical analyses of the primary and secondary endpoints.

Study	Primary Endpoint	Statistical Analysis methods
1	1.1 Positive and negative concordance of Omni compared to GeneXpert when Xpert MTB/RIF Ultra testing is done using clinical	Number of MTB culture positive specimens detected as MTB positive by Xpert MTB/RIF Ultra when using Omni and GeneXpert, respectively
	specimens	Number of MTB culture negative specimens detected as MTB negative by Xpert MTB/RIF Ultra when using Omni and GeneXpert, respectively
2	2 1.2 Positive and negative concordance of Omni compared to GeneXpert when Omni Xpert MTB/RIF testing is done at high environmental conditions	Number of MTB positive controls detected as MTB positive by Xpert MTB/RIF Ultra when testing Omni at different environmental conditions
		Number of MTB positive controls detected as MTB positive by Xpert MTB/RIF Ultra when testing Omni vs. GeneXpert at normal environmental conditions
		Number of RIF-resistant controls detected as RIF resistant by Xpert MTB/RIF Ultra when testing Omni at different environmental conditions
		Number of RIF-sensitive controls detected as RIF sensitive by Xpert MTB/RIF Ultra when testing Omni at different environmental conditions

Omni Bio-equivalency study

	Number of RIF-resistant controls detected as RIF resistant by Xpert MTB/RIF Ultra when testing Omni vs. GeneXpert at normal environmental conditionsNumber of RIF sensitive controls detected as RIF sensitive by Xpert MTB/RIF Ultra when testing Omni vs. GeneXpert at normal environmental conditions
1.3 Average difference in Ct-values for each Xpert MTB/RIF Ultra MTBC probe when testing on Omni compared to GeneXpert for MMQCI controls at different temperature and humidity conditions	Individual value plots of all Cts from each probe (SPC, IS1081-IS6110, rpoB1, rpoB2, rpoB3, rpoB4) from wildtype MMQCI control testing between GeneXpert and Omni when testing at normal environmental conditions.
	Individual value plots of all Cts from each probe (SPC, IS1081-IS6110, rpoB1, rpoB2, rpoB3, rpoB4) from mutant MMQCI control testing between GeneXpert and Omni when testing at normal environmental conditions.
	Individual value plots of all Cts from each probe (SPC, IS1081-IS6110, rpoB1, rpoB2, rpoB3, rpoB4) from wildtype MMQCI control testing between GeneXpert and Omni when testing at different environmental conditions.
	Individual value plots of all Cts from each probe (SPC, IS1081-IS6110, rpoB1, rpoB2, rpoB3, rpoB4) from mutant MMQCI control testing between GeneXpert and Omni when testing at different environmental conditions.
1.4 Average difference in Tm values for each Xpert MTB/RIF Ultra rpoB probe when testing on Omni compared to GeneXpert for MMQCI controls at different temperature and humidity conditions	Individual value plots of all Tms from each probe (SPC, IS1081-IS6110, rpoB1, rpoB2, rpoB3, rpoB4) from wildtype MMQCI control testing between GeneXpert and Omni when testing at normal environmental conditions.
	Individual value plots of all Tms from each probe (SPC, IS1081-IS6110, rpoB1, rpoB2, rpoB3, rpoB4) from mutant MMQCI control testing between GeneXpert and Omni when testing at normal environmental conditions.
	Individual value plots of all Tms from each probe (SPC, IS1081-IS6110, rpoB1, rpoB2, rpoB3, rpoB4) from wildtype MMQCI control testing between GeneXpert and Omni when testing at different environmental conditions.
	Individual value plots of all Tms from each probe (SPC, IS1081-IS6110, rpoB1, rpoB2, rpoB3, rpoB4) from mutant MMQCI control testing between GeneXpert and Omni when testing at different environmental conditions.

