8.2 Sample Size Determination

Objective 1.1 – Compare the performance of the Xpert MTB/RIF Ultra assay between the GeneXpert and Omni systems with testing of clinical specimens

Table 1. Sample size required to assess percent agreement between platforms at a given confidence interval width with 95% confidence.

		Width of Confidence Interval						
		5%	7.5%	10%	12.5%	15%	17.5%	20%
	99%	61	28	16	10	7	5	4
	97.5%	150	67	38	24	17	13	10
	95%	292	130	73	47	33	24	19
	92.5%	427	190	107	69	48	35	27
	90%	554	246	139	89	62	46	35
	87.5%	673	299	169	108	75	55	43
SL	85%	784	349	196	126	88	64	49
tform	82.5%	888	395	222	142	99	73	56
% Agreement between platforms	80%	984	438	246	158	110	81	62
	77.5%	1072	477	268	172	120	88	67
	75%	1153	513	289	185	129	95	73
seme	72.5%	1226	545	307	197	137	101	77
Agre	70%	1291	574	323	207	144	106	81
%	67.5%	1349	600	338	216	150	111	85
	65%	1399	622	350	224	156	115	88
	62.5%	1441	641	361	231	161	118	91
	60%	1476	656	369	237	164	121	93
	57.5%	1503	668	376	241	167	123	94
	55%	1522	677	381	244	170	125	96
	52.5%	1533	682	384	246	171	126	96

Omni Bio-equivalency study Protocol # TB046-bioequiv1.0

385 246 171 126 97

The GeneXpert and Omni platforms are anticipated to demonstrate equivalent performance for the testing for Xpert Ultra cartridges. Given a confidence level of 95%, a sample size of 150 would yield a confidence interval of 5% to determine 97.5% agreement between platforms. Testing 160 MTB positive sample size would ensure these parameters are met even given a 6.25% error/invalid rate.

Objective 1.2 – Compare the performance of the Xpert MTB/RIF Ultra assay between the GeneXpert and Omni systems with testing of MMQCI controls at high temperature and humidity conditions

		Width of Confidence Interval						
		5%	7.5%	10%	12.5%	15%	17.5%	20%
	99%	43	20	11	7	5	4	3
	97.5%	106	47	27	17	12	9	7
	95%	206	92	52	33	23	17	13
	92.5%	301	134	76	49	34	25	19
rms	90%	390	174	98	63	44	32	25
% Agreement between platforms	87.5%	474	211	119	76	53	39	30
	85%	552	246	138	89	62	46	35
	82.5%	625	278	157	100	70	52	40
	80%	693	308	174	111	77	57	44
green	77.5%	755	336	189	121	84	62	48
% A{	75%	812	361	203	130	91	67	51
	72.5%	864	384	216	139	96	71	54
	70%	910	405	228	146	102	75	57
	67.5%	950	423	238	152	106	78	60
	65%	985	438	247	158	110	81	62

Table 2. Sample size required to assess percent agreement between platforms at a given confidence interval width with 90% confidence.

Omni Bio-equivalency study

Protocol # TB046-bioequiv1.0

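### Section 8.1 analyses primary endpoint 1.1 by separate per-platform counts against culture, which bound but do not identify the Omni–GeneXpert agreement that the endpoint names and the sample size was set for

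*Protocol*

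**What the plan says.** Section 2 of the protocol gives the first primary outcome as "1.1 Positive and negative concordance of Xpert MTB/RIF Ultra testing on Omni compared to GeneXpert for clinical specimens".

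The design is paired. Under section 6.1, "each clinical specimen will be prepared, homogenized and split into two equal aliquots for Xpert MTB/RIF Ultra testing", and section 5.3 adds that "One cartridge will be tested using GeneXpert and one using Omni".

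Table 1 in section 8.2 is headed "Sample size required to assess percent agreement between platforms at a given confidence interval width with 95% confidence". The text below it takes 150 evaluable specimens at 97.5% agreement for an interval 5% wide, and raises this to 160 to allow for a 6.25% error/invalid rate.

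Section 8.1 lists two methods against endpoint 1.1:

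- "Number of MTB culture positive specimens detected as MTB positive by Xpert MTB/RIF Ultra when using Omni and GeneXpert, respectively"
- "Number of MTB culture negative specimens detected as MTB negative by Xpert MTB/RIF Ultra when using Omni and GeneXpert, respectively"

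For this endpoint it lists no cross-classification of the two results, no agreement proportion and no confidence interval. The same section states: "Given the study design, no detailed statistical analysis plan (SAP) will be prepared for this work". Dummy tables are promised but not shown.

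**The concern.** The endpoint and the sample size both ask how often the two platforms give the same result on the same specimen. The listed analysis asks how many culture-positive (or culture-negative) specimens each platform calls correctly, one platform at a time. Those are the margins of a two-by-two table, whereas concordance depends on its inner cells.

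Two platforms with the same totals may have called the same specimens or partly different ones. Followed as written, section 8.1 would yield equal or similar counts with no estimate of the primary endpoint and no interval around it, although an interval width was the whole justification for the sample size. Section 12 says the results go to WHO and to peer-reviewed journals. If the agreement measure, its denominator and the place of error/invalid runs are first chosen once the data are in hand, that choice is open to criticism.

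**Working it through.** **1. The plan's own figure.** Inputs from section 8.2: agreement p = 0.975, full interval width w = 0.05, 95% confidence (z = 1.96). For one proportion with a Wald interval:

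n = 4 z² p(1 − p) / w² = 4 × 1.96² × 0.975 × 0.025 / 0.05² = 149.8, rounded up to 150.

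With the error/invalid allowance: 150 / (1 − 0.0625) = 160. Both figures reproduce. This is a precision calculation for a single between-platform agreement proportion, not for two separate detection rates.

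**2. What the two totals determine.** Take n specimens in one culture stratum, with a positive on Omni, b positive on GeneXpert and k positive on both. Section 8.1 reports a and b. The number k is not reported and can be any whole number from max(0, a + b − n) to min(a, b). Then:

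- overall agreement = (n − a − b + 2k) / n
- Omni positivity among GeneXpert positives = k / b
- Omni-only minus GeneXpert-only specimens = a − b

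The third quantity is known from the totals; the first two depend on k.

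**3. Size among the 160 culture-positives.** The protocol states no expected Ultra detection rate for these specimens, so the counts below are assumed, equal on both platforms and without error/invalid runs.

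| Positive on each platform | Smallest k | Overall agreement | Omni positive among GeneXpert positive |
|---|---|---|---|
| 156 | 152 | 152/160 = 95% to 100% | 152/156 = 97.4% to 100% |
| 150 | 140 | 140/160 = 87.5% to 100% | 140/150 = 93.3% to 100% |
| 144 | 128 | 128/160 = 80% to 100% | 128/144 = 88.9% to 100% |

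**4. Against the planned precision.** With 150 evaluable specimens and 146 positive on each platform (97.3%), smallest k = 142. Overall agreement then lies between 142/150 = 94.7% and 100%. That undetermined span of 5.3 points is already slightly wider than the 5-point interval the study was sized for.

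**5. Culture-negatives.** With 38 of 40 negative on each platform (assumed), at least 36 are negative on both, so overall agreement lies between 36/40 = 90% and 100%.

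**6. Interval for the paired difference.** Its large-sample variance is [d − (a − b)²/n] / n², where d is the total number of discordant specimens. With 150 of 160 on each platform, the difference is 0 and d can be anything from 0 to 20. At d = 20 the 95% half-width is 1.96 × √20 / 160 = 0.055, or 5.5 points; at d = 0 this formula gives 0. The totals do not say which applies.

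**7. When the totals suffice.** If one platform detects all specimens in a stratum, or none, the smallest and largest k coincide and agreement is fixed.

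**The case against.** The strongest defence is that nothing is lost in the data. Every specimen is run on both platforms, the results are exported from both instruments, and section 8.1 describes itself as a summary of selected elements with dummy tables to follow. The row still carries concordance as the endpoint's name, so a cross-table may well have been intended. It stands that data, design and sample size are sound. It does not stand that the method can be left open: the method written beside the endpoint is a different quantity, and the protocol rules out a detailed SAP that might correct it.

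A reader might also infer stronger points that the documents do not support:

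- **That the totals say nothing about agreement.** They bound it, sometimes tightly. At 156 of 160 each, the worst case for Omni positivity among GeneXpert positives (97.4%) is about the 97.5% planning value.
- **That one-directional discordance would go unseen.** The difference between the totals equals the difference between the two discordant cells, so net direction is visible. What is missing is the total discordance.
- **That grouping by culture is itself wrong.** Specimens are selected by culture status and the 160 were sized as MTB-positives. The protocol does not define the denominator of positive or negative concordance, so agreement within culture strata is a legitimate reading.
- **That the plan would declare equivalence wrongly.** It states no equivalence criterion for endpoint 1.1, so no such decision rule can be said to fail.

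**Conclusion.** The point holds as a mismatch between the stated analysis and the endpoint. As written, section 8.1 does not estimate primary endpoint 1.1: its counts give the net difference in detection and a range for agreement, but neither the agreement itself nor an interval for it or for the paired difference.

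The size depends on how many specimens the platforms miss. For overall agreement the undetermined span is 5 points at 156 of 160 each, 12.5 points at 150 and 20 points at 144. For Omni positivity among GeneXpert positives it is 2.6, 6.7 and 11.1 points. These rest on assumed, equal detection counts; the span vanishes if one platform detects all or none. The sample size calculation is correct for an agreement proportion and is not in question.

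**What to change.** In section 8.1 and the matching dummy table:

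- State a per-specimen paired table of Omni by GeneXpert results within each culture stratum (160 culture-positive, 40 culture-negative), showing both discordant cells and the error/invalid runs on each side.
- Define the denominator of positive and of negative concordance: either the culture stratum or the GeneXpert result.
- Report each concordance with a 95% confidence interval, the level used for the sample size. The choice of interval method can be left to the statistician.
- Keep the per-platform counts against culture as supporting description.

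The cost is a rewording of one row in section 8.1 and one dummy table. It needs no new data, no extra testing and no change in sample size.
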